A total of 96 statistical tests will be conducted in Phase 1 (not including supplemental age-stratified analyses). To account for the possibility of falsely detecting a significant result (i.e. Type 1 error) arising from multiple statistical tests, we will control for the False Discovery Rate (FDR) using the Benjamini-Hochberg procedure (assuming a two-tailed test and FDR of 0.05)¹. The Benjamini-Hochberg procedure involves ranking all the p-values from a family of tests from smallest to largest. The smallest p-value has a rank of $i=1$, the next smallest has $i=2$, etc. The next step is comparing each individual p-value to its Benjamini-Hochberg critical value, $(i/m)Q$, where i is the rank, m is the total number of tests, and Q is the FDR you choose. The largest p-value that has $P < (i/m)Q$ is statistically significant, and all of the p-values smaller than it are also statistically significant, even the ones that are not less than their Benjamini-Hochberg critical value. In other words, once a p-value in the list satisfies $P \geq (i/m)Q$, then no other p-values of that value or larger are considered statistically significant (and all less than that value are statistically significant).

There is little guidance on the best FDR to use in a study. Note that for an FDR of 0.05, the smallest p-value needs to be less than what would be the conservative Bonferonni correction (0.05/m), i.e., when $i=1$, then the Benjamini-Hochberg critical value is $(1/m)*0.05$. At an FDR of 0.05, the Benjamini-Hochberg critical value becomes slightly less conservative than a Bonferonni cut-off if p-values are less than this cut-off. However, if no p-values are less than 0.05/m, then no results are statistically significant. Thus, an FDR of 0.05 is conservative, like a Bonferonni correction. Accordingly, we will report results indicating statistical significance using an FDR of 0.05 (most conservative) and using no adjustment for multiple comparisons (least conservative).

We do not anticipate substantial item non-response, nor do we expect that patterns of item non-response would vary significantly among study conditions. Thus, we will plan to use pairwise deletion to include all available data for each particular analysis. We will examine the data for issues of item non-response and differential item non-response and adjust our approach for handling missing data accordingly.

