For those statements which have multiple corresponding belief items that can be scaled into a single continuous variable, we will test these hypotheses using linear regression. For statements with single ordinal Likert-type belief items or for which multiple items are not scalable, we are testing hypotheses of the form that treatment (being exposed to GHW) is associated with a greater pre-post change in level of the ordinal dependent variable than being in the control group (being exposed to an SG warning). Thus, for these items we will use ordinal logistic regression. All regressions, both logistic and linear will be estimated in Stata version 14.1 and will be estimated using Stata's robust standard errors.

In the cases where the dependent variable is continuous and a linear regression model is estimated, the interaction term (Session*Condition) represents the difference in difference of the means or treatment effect. However, in a non-linear model, such as when the dependent variable is ordered and we estimate an ordinal regression model, the coefficient of the interaction term is not a direct measure of the treatment effect due to the non-linear model. As noted in Puhani (2012), in a non-linear model with a strictly monotonic transformation function of a linear index, the sign of the coefficient of the interaction term is equal to the sign of the treatment effect. Testing the significance of the interaction term in the non-linear model is best done via bootstrapping (Puhani, 2012).

As a supplement to the analyses above, we will conduct parallel analyses stratified by age group (i.e. youth aged 13-17; young adults aged 18-24; and adults aged 25+) and smoking status (current smoker versus non-smoker), to examine potential effects within each age and smoking status group. Of note is that this study is not sufficiently powered to detect within-age or

smoking status group differences, and so results from the stratified analyses should be interpreted with caution (i.e., a non-significant finding within an age or smoking status group may reflect lack of statistical power).

A total of 16 statistical tests will be conducted in Phase 2 (not including supplemental age-stratified analyses). To account for the possibility of falsely detecting a significant result (i.e. Type 1 error) arising from multiple statistical tests, we will control for the False Discovery Rate (FDR) using the Benjamini-Hochberg procedure (assuming a two-tailed test and FDR of 0.05).

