aged 13-17; young adults aged 18-24; and adults aged 25+) and Smoking Status is an indicator for current smoking versus not current smoking (in the adult and young adult samples non-current smokers are never smokers and in the youth sample non-current smokers are those youth susceptible to smoking). These models will include covariates for age and smoking status group to account for potential associations between age, smoking status and outcomes of interest. The coefficient from the Condition variable indicates whether accurate warning recall was significantly greater among those exposed to a GHW as compared to those exposed to a SG warning. This general model will be repeated for each of 16 treatment versus control group comparisons. All regressions will be estimated in Stata version 14.1 and will be estimated using Stata's robust standard errors.

As a supplement to the analyses above, we will conduct parallel analyses stratified by age and smoking status group, to examine potential effects within each age and smoking status group. Of note is that this study is not sufficiently powered to detect within-age or smoking status-group differences, and so results from the stratified analyses should be interpreted with caution (i.e. a non-significant finding within an age or smoking status group may reflect lack of statistical power).

A total of 16 statistical tests will be conducted in Phase 3 (not including supplemental age-stratified analyses). To account for the possibility of falsely detecting a significant result (i.e. Type 1 error) arising from multiple statistical tests, we will control for the False Discovery Rate (FDR) using the Benjamini-Hochberg procedure (assuming a two-tailed test and FDR of 0.05) (Benjamini & Hochberg, 1995).

We do not anticipate substantial item non-response, nor do we expect that patterns of item non-response would vary significantly among study conditions. Thus, we will plan to use pairwise deletion to include all available data for each particular analysis. We will examine the data for issues of item non-response and differential item non-response and adjust our approach for handling missing data accordingly.

References

Benjamini, Y. & Hochberg Y. (1995). Controlling the false discovery rate: A practical and powerful approach to multiple testing. *J Roy Stat Soc. Series B*, 57(1), pp. 289–300.

Cronbach, L. J. (1951). Coefficient alpha and the internal structure of tests. *psychometrika*, 16(3), 297-334.

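### The SAP states the Benjamini-Hochberg step-up rule correctly, then restates it as a stricter stop-at-first-failure rule that can remove discoveries in any phase

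*SAP*

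**What the plan says.** SAP section 4.1 controls the false discovery rate (FDR) with the Benjamini-Hochberg procedure, "assuming a two-tailed test and FDR of 0.05". It ranks the p-values from smallest to largest and compares the i-th with (i/m)Q. It then makes three statements about how to decide:

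- **Step-up.** The largest p-value below its critical value is significant, and so is every smaller one, "even the ones that are not less than their Benjamini-Hochberg critical value".
- **Restatement.** The next sentence, introduced by *In other words*, says that once a p-value in the list is at or above its critical value, "then no other p-values of that value or larger are considered statistically significant".
- **Entry condition.** The following paragraph says that "if no p-values are less than 0.05/m, then no results are statistically significant".

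From the third statement the SAP infers that an FDR of 0.05 is about as conservative as a Bonferroni correction. *Accordingly*, it will report Phase 1 significance "using an FDR of 0.05 (most conservative) and using no adjustment for multiple comparisons (least conservative").

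The families are counted separately: "A total of 96 statistical tests will be conducted in Phase 1", "A total of 16 statistical tests will be conducted in Phase 2" and "A total of 16 statistical tests will be conducted in Phase 3". Sections 4.2 and 4.3 name the same procedure at the same FDR but do not describe it again, so section 4.1 holds the only operational definition.

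**The concern.** The step-up sentence keeps a p-value that misses its own cut-off, provided a larger p-value passes. The sentence meant to paraphrase it excludes that same p-value and everything above it. Both cannot hold. The entry condition repeats the error: it is true of the restated rule and false of Benjamini-Hochberg.

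A prespecified plan should give one answer for one set of p-values, and this one supports two. An analyst who codes the restatement would discard warnings that the named procedure declares significant. The comparison with Bonferroni also sits badly with SAP section 3, which prefers FDR control because it has more power than family-wise methods.

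**Working it through.** **1. The plan's own figures.** Table 4 lists 6 outcomes, each with 16 comparisons: 6 × 16 = 96, as stated. The rank-1 critical value is 0.05/96 = 0.000521 in Phase 1 and 0.05/16 = 0.003125 in Phases 2 and 3. The SAP is right that this equals the Bonferroni cut-off. The error lies in making it a condition for any rejection.

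**2. The rules side by side.** Let p(1) ≤ … ≤ p(m) and c(i) = (i/m) × 0.05.

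- Step-up: k = the largest i with p(i) < c(i); reject 1 to k.
- First failure: k = (the smallest i with p(i) ≥ c(i)) − 1; reject 1 to k.
- Entry gate: apply step-up only if p(1) < c(1).

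The first-failure k can never exceed the step-up k, so the restatement can only remove discoveries. If p(1) ≥ c(1), the first-failure k is 0. The entry gate therefore follows from the first-failure rule, but not from step-up.

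**3. Worked lists, m = 16.** The first critical values are 0.003125, 0.00625 and 0.009375; the last is 0.05.

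| p-values | Step-up | First failure | Step-up with gate |
|---|---|---|---|
| 0.0035, 0.005, 0.008, 13 × 0.5 | 3 | 0 | 0 |
| 0.001, 0.007, 0.008, 13 × 0.5 | 3 | 1 | 3 |
| 16 × 0.04 | 16 | 0 | 0 |

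In the first list, 0.0035 fails at rank 1 but 0.008 < 0.009375 passes at rank 3. In the second, 0.007 fails at rank 2 and 0.008 passes at rank 3. In the third, 0.04 < 0.05 passes at rank 16. No p-value there would survive Bonferroni, yet step-up rejects all 16. An FDR of 0.05 is therefore not equivalent to a Bonferroni correction.

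**4. How often it would matter.** Inputs from SAP section 3: 2,080 control and 480 per treatment arm at Session 1; 50% retention, so 1,040 and 240 at Session 2; effect 0.3; SD 1; within-person correlation ρ, taken here from 0 to 0.4.

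- Phase 2: SE = √[2(1 − ρ)(1/1,040 + 1/240)]. At ρ = 0 this is 0.1013, so z = 0.3/0.1013 = 2.96. At ρ = 0.4 it is 0.0784, so z = 3.82.
- Phase 1: SE = √(1/2,080 + 1/480) = 0.0506 SD. A 0.3 SD effect would give z = 5.9. A z of 1.5 to 2 corresponds to only about 0.08 to 0.10 SD.
- Two comparisons sharing the control have correlation 240/(1,040 + 240) = 0.1875. It is the same at Session 1, because the allocation ratio is unchanged.

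As a check on the planning model, the same formula reproduces 18 of the 25 unadjusted powers in Table 3 to within 2 points. The other 7 differ by 3 to 8 points, which is within about 2.1 Monte Carlo standard errors for 100 simulations.

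Simulated share of families in which step-up and first failure give different results:

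| Family | Effects | Share that differ |
|---|---|---|
| 16 tests | 0.3 at Session 2; ρ 0 to 0.4; 4, 8 or 16 real effects | 0.1% to 3.1% |
| 16 tests | assumed mean z 1.5 to 2; half or all real | about 4% to 10% |
| 96 tests | assumed mean z 1.5 to 2; half or all real | about 12% to 24% |
| 96 tests | assumed mean z 2.96 | about 1% to 3% |
| 96 tests | assumed mean z 5.9 | about 0.1% or less |

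At the planning effect, average power per test falls by at most about 1.5 points (for example 0.633 to 0.618 with ρ = 0 and 4 real effects). At smaller assumed effects of 0.1 to 0.2, it falls by up to about 2 points. The entry gate alone changes the result in 0% to about 4% of 16-test families.

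**The case against.** The best defence is that the governing rule is present and correct. The SAP names the procedure, gives its critical value and states step-up unmistakably, including the clause about p-values that miss their own cut-off. The faulty sentence is offered as a paraphrase, and the 0.05/m remarks are commentary on the choice of Q. A standard software routine would apply step-up, and at the planning effect the two rules seldom disagree.

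All of this limits the size of the problem and is accepted. It does not remove the contradiction. The wrong rule appears in two mutually consistent forms, and nothing elsewhere in the SAP corrects it.

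Three stronger readings are tempting but not supported:

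- *The error will change the results.* It can; whether it does depends on the observed p-values and on which sentence is coded.
- *It inflates false discoveries.* It does not; both restatements err in the conservative direction.
- *It makes the unadjusted Phase 1 report improper, with 96 × 0.05 = 4.8 false positives to be expected.* That figure requires all 96 null hypotheses to be true. The dual report is prespecified, labelled by how conservative each version is, and stated only for Phase 1. Only the reason given for it fails.

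**Conclusion.** The concern holds as an internal contradiction in the definition of significance, with a false corollary about 0.05/m. It reaches all three phases, because the later sections rely on the definition in section 4.1.

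Its practical size is modest: about 0.1% to 3% of 16-test families at the planning effect. It becomes appreciable only if effects are weak, at about 4% to 10% of 16-test and 12% to 24% of 96-test families.

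These shares rest on normal test statistics, 50% retention at Session 2 and the shared-control correlation. For 96 tests they also assume that the six outcomes are independent within an arm. The SAP gives no Phase 1 effect sizes, so the mean z values there are assumptions, as is carrying the 0.3 belief-change effect over to Phase 1. The contradiction itself needs none of these assumptions. It should be fixed, but it does not undermine the error control that the plan promises.

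**What to change.** In SAP section 4.1:

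- Delete the sentence that begins *In other words*.
- Delete the statements that the smallest p-value must be below 0.05/m and that otherwise nothing is significant.
- Delete the inference that an FDR of 0.05 is like a Bonferroni correction.
- Keep one rule: find the largest i with p(i) ≤ (i/m)Q and reject hypotheses 1 to i; if there is no such i, reject none.
- Remove *Accordingly* and the reasoning behind it as the ground for dual reporting. Whether unadjusted results are also shown is a separate reporting choice that needs its own reason.

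Add a cross-reference to this rule in sections 4.2 and 4.3. The cost is SAP wording only; no sample size, model or data collection changes.

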4.2. Phase 2 Analysis: Condition-level Comparisons of Change in Beliefs

Model 1: Change in Beliefs from Session 1 to Session 2

For the Phase 2 analysis, we will conduct treatment vs. control comparisons of change in beliefs about the negative health consequences of smoking contained in the warnings. Note that participants in the control condition will be exposed to a random selection of one of four Surgeon General’s (SG) warnings; thus, each analysis will compare the change in belief scores between a particular treatment condition and the control group as averaged across the four SG warnings (i.e., we will compare treatment scores to a single control group score, rather than conducting separate analyses for each SG warning within the control condition).

For each experimental condition, the survey includes an item or series of items in which respondents are asked to rate their level of agreement with a statement about a negative health consequence corresponding to the warning for that condition. The number of items associated with a particular warning ranges from 1 to 4. These items are assessed once during Session 1 before stimuli exposure, and then again following second stimuli exposure in Session 2. Table 5 provides a summary of the comparisons, dependent variables, and analysis approach for each of the Phase 2 analyses.

Table 5. Phase 2 Analyses

Analysis #	Comparison	Dependent Variable(s) [All 5-level “Strongly disagree” to “Strongly agree” response options]	Analysis
-------------------	-------------------	---	-----------------

1	Condition 1 vs. Control (0)	A1_1. Cigarettes are addictive	Ordinal logistic regression
2	Condition 2 vs. Control (0)	A2_1. Tobacco smoke can harm your children	Ordinal logistic regression
3	Condition 3 vs. Control (0)	A3_1. Smoking can kill you	Ordinal logistic regression
4	Condition 4 vs. Control (0)	A4_1. Smoking causes fatal lung disease in nonsmokers	Ordinal logistic regression
5	Condition 5 vs. Control (0)	A5_1. Quitting smoking now greatly reduces serious risks to your health	Ordinal logistic regression
6	Condition 6 vs. Control (0)	A6_1. Smoking causes head cancer A6_2. Smoking causes neck cancer	Linear regression (if scaled); ordinal logistic regression (if items treated separately)
7	Condition 7 vs. Control (0)	A7_1. Smoking causes bladder cancer, which can lead to bloody urine A7_2. Smoking causes bladder cancer	Linear regression (if scaled); ordinal logistic regression (if items treated separately)
8	Condition 8 vs. Control (0)	A8_1. Smoking during pregnancy stunts fetal growth	Ordinal logistic regression
9	Condition 9 vs. Control (0)	A9_1. Smoking causes heart disease A9_2. Smoking causes strokes A9_3. Smoking clogs arteries A9_4. Smoking clogs arteries, which causes heart disease A9_5. Smoking clogs arteries, which causes strokes	Linear regression (if scaled); ordinal logistic regression (if items treated separately)
10	Condition 10 vs. Control (0)	A10_1. Smoking causes COPD, a lung disease that can be fatal A10_2. Smoking causes COPD A10_3. Smoking causes a lung disease that can be fatal	Linear regression (if scaled); ordinal logistic regression (if items treated separately)
11	Condition 11 vs. Control (0)	A10_1. Smoking causes COPD, a lung disease that can be fatal A10_2. Smoking causes COPD	Linear regression (if scaled); ordinal logistic regression

		A10_3. Smoking causes a lung disease that can be fatal	regression (if items treated separately)
12	Condition 12 vs. Control (0)	A12_1. Smoking reduces blood flow, which can cause erectile dysfunction A12_2. Smoking reduces blood flow A12_3. Smoking can cause erectile dysfunction	Linear regression (if scaled); ordinal logistic regression (if items treated separately)
13	Condition 13 vs. Control (0)	A13_1. Smoking reduces blood flow to the limbs, which can require amputation A13_2. Smoking reduces blood flow to the limbs A13_3. Smoking can lead to amputation	Linear regression (if scaled); ordinal logistic regression (if items treated separately)
14	Condition 14 vs. Control (0)	A14_1. Smoking causes type 2 diabetes, which raises blood sugar. A14_3. Smoking can cause Type 2 Diabetes	Linear regression (if scaled); ordinal logistic regression (if items treated separately)
15	Condition 15 vs. Control (0)	A15_1. Smoking causes age-related macular degeneration, which can lead to blindness A15_2. Smoking causes age-related macular degeneration A15_3. Smoking can lead to blindness	Linear regression (if scaled); ordinal logistic regression (if items treated separately)
16	Condition 16 vs. Control (0)	A16_1. Smoking causes cataracts, which can lead to blindness A16_2. Smoking causes cataracts	Linear regression (if scaled); ordinal logistic regression (if items treated separately)

The items being used to measure beliefs have Likert-type response scales. Conceptually, the response categories for a Likert response scale represent an underlying belief continuum. For warning statements with multiple corresponding items, we will assess whether to scale the items, using the following protocol:

- 1) Run a test of internal consistency reliability using Cronbach's alpha (Cronbach, 1951) on all of the items in a domain. If the test indicates "modest" reliability of $\alpha \geq 0.70$ (Nunnally & Bernstein, 1994), scale the items.

- 2) If $\alpha < 0.70$, but all item-total correlations (i.e. the correlation between the item score and the overall scale score) are ≥ 0.4 , scale the items (Item-total correlations of between 0.30—0.40 and greater have been suggested as sufficiently discriminating (Nunnally & Bernstein, 1994; Traub, 1994; Leong & Austin, eds., 2006)
- 3) If criteria 1 and 2 are not met, determine whether the scale alpha would increase to ≥ 0.70 if any items were deleted from the scale (i.e. using Stata’s “alpha” command with “item” option specified). If the alpha value threshold would be met by dropping an item or items:
 - a. Drop those items to form a scale with $\alpha \geq 0.70$
 - b. Also run analyses of each item individually
- 4) Otherwise, run analyses of each item individually

We are measuring beliefs at each study session. The above procedure to inform the scaling of the belief items will be made on the beliefs assessed at Session 1 (baseline) and then applied to the beliefs measured at the remaining sessions. We do not expect the measurement structure of beliefs to change over a longitudinal sample over a relatively short period of time. Assuming attrition across study sessions, basing the measurement structure on the Session 1 sample utilizes the largest available sample.

To determine the GHW’s immediate impact on targeted beliefs, we will examine the extent to which pre-post differences in beliefs vary between those exposed to GHW (treatment) and SG warnings (control). The general form of this analysis approach is as follows:

$$(\text{Belief}^T_{S2} - \text{Belief}^T_{S1}) - (\text{Belief}^C_{S2} - \text{Belief}^C_{S1})$$

where Belief represents the average value (for continuous variables) or probability of being in a higher response category (for ordinally-treated variables), among those in a Treatment (*T*) or Control (*C*) group, at Session 2 (*S2*) or Session 1 (*S1*).

For each treatment versus control comparison, will test hypotheses of the following general form:

- H_0 : Average pre-post difference in belief score for those in the treatment condition = average pre-post difference in belief score in the control condition
- H_a : Average pre-post difference in belief score for those in the treatment condition \neq average pre-post difference in belief score in the control condition

To test the hypotheses for Phase 2 analyses, for each outcome we will estimate a regression model of the following general form:

$$\text{Belief} = f(\text{Condition}, \text{Session}, \text{Condition}*\text{Session}, \text{Age}, \text{Smoking Status})$$

where Belief is a measure of agreement with a statement (or set of statements) about the health effects of cigarette smoking, Condition is a dichotomous indicator for a treatment versus control condition, Session is a dichotomous indicator for Session 2 versus Session 1, Condition*Session is the interaction between study condition and study session, Age is a categorical variable for age group (i.e. youth aged 13-17; young adults aged 18-24; and adults aged 25+), and Smoking Status is an indicator for current smoking versus not current smoking (in the adult and young adult samples non-current smokers are never smokers and in the youth sample non-current smokers are those youth susceptible to smoking). These models will include covariates for age and smoking status group to account for potential associations between age, smoking status and outcomes of interest. The key variable of interest in these models is the interaction term, Condition*Session. The coefficient on Condition*Session indicates whether the pre-post change in belief was greater among respondents exposed to a GHW as compared to those exposed to a SG warning. This general model will be repeated for each of 16 treatment versus control group comparisons.

For those statements which have multiple corresponding belief items that can be scaled into a single continuous variable, we will test these hypotheses using linear regression. For statements with single ordinal Likert-type belief items or for which multiple items are not scalable, we are testing hypotheses of the form that treatment (being exposed to GHW) is associated with a greater pre-post change in level of the ordinal dependent variable than being in the control group (being exposed to an SG warning). Thus, for these items we will use ordinal logistic regression. All regressions, both logistic and linear will be estimated in Stata version 14.1 and will be estimated using Stata's robust standard errors.

In the cases where the dependent variable is continuous and a linear regression model is estimated, the interaction term (Session*Condition) represents the difference in difference of the means or treatment effect. However, in a non-linear model, such as when the dependent variable is ordered and we estimate an ordinal regression model, the coefficient of the interaction term is not a direct measure of the treatment effect due to the non-linear model. As noted in Puhani (2012), in a non-linear model with a strictly monotonic transformation function of a linear index, the sign of the coefficient of the interaction term is equal to the sign of the treatment effect. Testing the significance of the interaction term in the non-linear model is best done via bootstrapping (Puhani, 2012).

As a supplement to the analyses above, we will conduct parallel analyses stratified by age group (i.e. youth aged 13-17; young adults aged 18-24; and adults aged 25+) and smoking status (current smoker versus non-smoker), to examine potential effects within each age and smoking status group. Of note is that this study is not sufficiently powered to detect within-age or

smoking status group differences, and so results from the stratified analyses should be interpreted with caution (i.e., a non-significant finding within an age or smoking status group may reflect lack of statistical power).

A total of 16 statistical tests will be conducted in Phase 2 (not including supplemental age-stratified analyses). To account for the possibility of falsely detecting a significant result (i.e. Type 1 error) arising from multiple statistical tests, we will control for the False Discovery Rate (FDR) using the Benjamini-Hochberg procedure (assuming a two-tailed test and FDR of 0.05).

We expect some level of overall attrition between Session 1 and Sessions 2 and 3. Although unlikely given the nature of the experimental procedure, there is a potential that the rate of attrition could vary between treatment and control groups, resulting in biased estimates of the effect of the GHWs. To assess potential problems resulting from differential attrition, we will calculate and report rates of overall attrition (i.e., the proportion of Session 1 participants randomly assigned to a treatment or control group for whom Session 2 / Session 3 data are not available) and differential attrition (i.e., the difference in attrition rates between treatment and control groups). We will report overall and differential rates of attrition for each of 16 treatment groups, assessed at Session 2 and Session 3. We have no *a priori* threshold for determining an acceptable level of attrition bias. Nevertheless, to contextualize findings, we can compare attrition rates to benchmarks for randomized controlled trials established by the Department of Education’s What Works Clearinghouse (Deke et al., 2015).

We do not anticipate substantial item non-response, nor do we expect that patterns of item non-response would vary significantly among study conditions. Thus, we will plan to use pairwise deletion to include all available data for each particular analysis. We will examine the data for issues of item non-response and differential item non-response and adjust our approach for handling missing data accordingly.

Model 2: Change in Beliefs at Session 3

To determine the GHW’s sustained impact on targeted beliefs, we will conduct parallel analyses to the Model 1 analyses described above, but with a Session indicator variable that indicates Session 3 versus Session 1 (as opposed to Session 2 vs. Session 1). The general form of this analysis approach is as follows:

$$(\text{Belief}^T_{S3} - \text{Belief}^T_{S1}) - (\text{Belief}^C_{S3} - \text{Belief}^C_{S1})$$

where belief represents the average value (for continuous variables) or probability of being in a higher response category (for ordinally-treated variables), among those in a Treatment (*T*) or Control (*C*) group, at Session 3 (*S3*) or Session 1 (*S1*).

The specific functional form of these models, hypothesis tests, and interpretation of coefficients are identical to those described for Model 1, with the exception that with Model 2 we are examining differences in Session 3 versus Session 1 belief values.

